3.5.3 Central Pathology Review

To ensure consistent diagnosis of PTCL subtypes, a panel of pathologists with appropriate expertise will review pathology slides from archival tumor specimens or biopsy as applicable. The techniques, such as immunohistochemistry staining, will be according to standard of practice using agreed methodology, no later than the end of study.

3.5.4 Independent Overall Efficacy Review

To ensure consistent overall efficacy review method is applied to assess disease response across the entire study, designated independent oncologists will review sequential clinical data of individual patients including radiological assessment provided by the independent radiological review. They will assign response outcome including best response, dates of initial response and progression when applicable, based on Cheson Criteria 2014.

4.0 QUALITY CONTROL AND QUALITY ASSURANCE

According to the Guidelines of Good Clinical Practice (GCP) (CPMP/ICH/135/95), the sponsor is responsible for implementing and maintaining quality assurance and quality control systems with written Standard Operating Procedures (SOPs).

Quality control will be applied to each stage of data handling.

The following steps will be taken to ensure the accuracy, consistency, completeness, and reliability of the data:

- Clinical laboratory parameters
- Study site initiation visit
- Early site visits post-enrollment
- Routine site monitoring
- Ongoing site communication and training
- Data management quality control checks
- Continuous data acquisition and cleaning
- Internal review of data
- Quality control check of the clinical study report (CSR)

In addition, sponsor may conduct periodic audits of the study processes, including, but not limited to study site, site visits, clinical laboratories, vendors, clinical database, and final CSR. When audits are conducted, access must be authorized for all study related documents including medical history and concomitant medication documentation to authorized sponsor's representatives and regulatory authorities.

4.1 Monitoring

The sponsor has engaged the services of a contract research organization, [REDACTED], to perform all monitoring functions within this clinical study. [REDACTED]

[REDACTED]' monitors will work in accordance with [REDACTED]' SOPs and have the same rights and responsibilities as monitors from the sponsor organization. Monitors will establish and maintain regular contact between the investigator and the sponsor.

Monitors will evaluate the competence of each study site, informing the sponsor about any problems relating to facilities, technical equipment or medical staff. During the study, monitors will check that written informed consent has been obtained from all patients correctly and that data are recorded correctly and completely. Monitors are also entitled to compare entries in eCRFs with corresponding source data and to inform the investigator of any errors or omissions. Monitors will also control adherence to the protocol at the study site. They will arrange for the supply of investigational product and ensure appropriate storage conditions are maintained.

Monitoring visits will be conducted according to all applicable regulatory requirements and standards. Regular monitoring visits will be made to each site while patients are enrolled in the study. The monitor will make written reports to the sponsor on each occasion contact with the investigator is made, regardless of whether it is by phone or in person.

During monitoring visits, entries in the eCRFs will be compared with the original source documents (source data verification). For the following items, this check will be 100%:

- Subject number
- Patient consent obtained
- Patient eligibility criteria (inclusion and exclusion criteria)
- Efficacy variables
- Medical record of AE

4.2 Data Management/Coding

Data generated within this clinical study will be handled according to the relevant SOPs of the Data Management and Biostatistics departments of [REDACTED].

Electronic Data Capture (EDC) will be used for this study, meaning that all eCRF data will be entered in electronic forms at the study site. Data collection will be completed by authorized study site staff designated by the investigator. Appropriate training and security measures will be completed with the investigator and all authorized study site staff prior to the study being initiated and any data being entered into the system for any study patients.

All data must be entered in English. The eCRFs should always reflect the latest observations on the patients participating in the study. Therefore, the eCRFs are to be completed as soon as possible during or after the patient's visit.

The investigator must verify that all data entries in the eCRFs are accurate and correct. If some assessments are not done, or if certain information is not available or not applicable or unknown, the investigator should indicate this in the eCRF. The investigator will be required to electronically sign off on the clinical data.

The monitor will review the eCRFs and evaluate them for completeness and consistency. The eCRF will be compared with the source documents to ensure that there are no discrepancies between critical data. All entries, corrections and alterations are to be made by the responsible investigator or his/her designee. The monitor cannot enter data in the eCRFs. Once clinical data of the eCRF have been submitted to the central server, corrections to the data fields will be audit trailed, meaning that the reason for change, the name of the person who performed the change, together with time and date will be logged. Roles and rights of the site staff responsible for entering the clinical data into the eCRF will be determined in advance. If additional corrections are needed, the responsible monitor or Data Manager will raise a query in the EDC application. The appropriate study centre staff will answer queries sent to the investigator. This will be audit trailed by the EDC application meaning that the name of investigational staff, time and date stamp are captured.

The eCRF is essentially considered a data entry form and should not constitute the original (or source) medical records unless otherwise specified. Source documents are all documents used by the investigator or hospital that relate to the patient's medical history, that verify the existence of the patient, the inclusion and exclusion criteria and all records covering the patient's participation in the study. They include laboratory notes, electrocardiogram (ECG) results, memoranda, pharmacy dispensing records, patient files, etc.

The investigator is responsible for maintaining source documents. These will be made available for inspection by the study monitor at each monitoring visit. The investigator must submit a completed eCRF for each patient who receives study medication, regardless of duration. All supportive documentation submitted with the eCRF, such as laboratory or hospital records, should be clearly identified with the study and patient number. Any personal information, including patient name, should be removed or rendered illegible to preserve individual confidentiality.

eCRF records will be automatically appended with the identification of the creator, by means of their unique UserID. Specified records will be electronically signed by the investigator to document his/her review of the data and acknowledgement that the data are accurate. This will be facilitated by means of the investigator's unique UserID and password; date and time stamps will be added automatically at time of electronic signature. If an entry on an eCRF requires change, the correction should be made in accordance with the relevant software procedures. All changes will be fully recorded in a protected audit trail, and a reason for the change will be required.

Adverse events will be coded using Medical Dictionary for Regulatory Activities (MedDRA) Version 21.1 Concomitant medications will be coded using WHO-DDE. Concomitant diseases/medical history will be coded using MedDRA.

4.3 Retention of Records

Records and documents pertaining to the conduct of this study and the distribution of IMP, including eCRFs, ICFs, laboratory test results, and medication inventory records, must be retained by the Principal investigator (Japan: Head of study site) for at least 15 years after completion or discontinuation of the study, or for the length of time required by relevant national or local health authorities, whichever is longer. After that period of time, the documents may be destroyed, pertinent to local regulations. No records may be disposed of without the written approval of the sponsor. Written notification should be provided to the sponsor prior to transferring any records to another party or moving them to another location.

4.4 Quality Assurance Audit

Study sites, the study database and study documentation may be subjected to Quality Assurance audit during the course of the study by the sponsor or delegate(s) on behalf of the sponsor. In addition, inspections may be conducted by regulatory bodies at their discretion.

4.5 Site Audits

The principal investigator or sub-investigators and institutions involved in the study will permit study-related monitoring, audits, IRB review, and regulatory inspection(s) by providing direct access to all study records. In the event of an audit, the principal investigator or sub-investigator agrees to allow the sponsor, its representatives, or the regulatory agencies access to all study records.

The investigator should promptly notify the sponsor or its authorized representative of any audits scheduled by any regulatory authorities and promptly forward copies of any audit reports received to the sponsor or its authorized representative.

5.0 STATISTICS

5.1 General Statistical Considerations

Protocol HBI-8000-203 is an open-label, Phase 2b pivotal study evaluating HBI-8000 for regulatory approval in Japan and South Korea for the indication of relapsed or refractory PTCL. The main analysis will be conducted for the purpose of regulatory submission of this product. The data cut-off (DCO) for the main analysis is set at the time when the last patient completes at least one post-efficacy assessment. The eCRF data by the DCO needs to be cleaned to have no unresolved queries. All independent reviews (including the Central Pathology Review, the independent radiological review, the Independent Overall Efficacy Review and review by the Data Safety Monitoring Board) by the DCO need to be completed before the main analysis. The data after the main analysis will be provided at the end of the study as a supportive material.

Statistical analysis for all safety, efficacy, and PK parameters will be primarily descriptive in nature. Categorical variables will be summarized by frequency distributions (number and percentages of patients), continuous variables will be summarized by mean, standard deviation, median, minimum, maximum, and time-to-event variables will be summarized using Kaplan-Meier methods and figures for the estimated median time.

All analyses, summaries, and listings will be performed using SAS software (version 9.3 or higher)

A detailed methodology for summary and statistical analysis of the data collected in this trial will be documented in a Statistical Analysis Plan (SAP) that will be dated and maintained by HUYABIO. The SAP may modify the plans outlined in the protocol; however, any major modifications of the primary endpoint definition and/or its analysis will also be reflected in a protocol amendment.

5.2 Determination of Sample Size

For efficacy determination, 40 patients evaluable for efficacy per protocol criteria are required. To ensure meeting this target, an estimated 50 to 60 patients would be enrolled in anticipation that some patients may not complete study treatment. Enrolled patients will be treated with the starting dose of 40 mg BIW to provide an assessment of tumor response as well as additional safety data. It is planned that 34 to 40 patients (27 evaluable patients) will be coming from Japan and 16 to 20 patients (13 evaluable patients) will be coming from Korea.

The target best ORR for this study is 30%, on the basis of the ORR results that were obtained in study TG0902CDM. The 95% confidence interval (CI) for an ORR of 30% at a sample size of N=40 is expected to be between 15.8% and 44.2%.

The power for showing the response rate >10% at 5% two-sided alpha in 40 patients is 89%.

The 95% confidence interval for an objective response rate (assumed to be 30%) at various sample sizes are shown below:

ORR (expected)	N	95% CI
30%	25	(12.0 – 48.0)
	30	(13.6 – 46.4)
	35	(14.8 – 45.2)
	40	(15.8 – 44.2)

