Disease diagnosis including histological subtypes will be confirmed by central pathology review conducted by independent pathologists.	
Efficacy should be analyzed using Full analysis set (FAS) and Per protocol set (PPS). The FAS is defined as Patients meeting all eligibility criteria and having received at least one dose of study medication, and at least one efficacy assessment of disease with either imaging studies or clinical examination after receiving study medication.	
The PPS is defined as Patients meeting all eligibility criteria and having completed Cycle 1 treatment or discontinued study treatment during cycle 1 due to clinical PD. It should be noted that the PPS includes subjects who discontinue within Cycle 1 due to clinical PD without imaging studies to assess disease status.	
In addition, Patients who are assessed as Non-PTCL by the central pathology review committee should be excluded from the FAS and PPS for efficacy. The non-PTCL subjects will be included in safety analysis for the study.	
The primary efficacy analysis is conducted in the PPS. The Efficacy analysis using the FAS will be also reported.	
It is estimated that 40 evaluable patients are adequate to provide efficacy assessment. Assuming a 30% ORR in this population of 40 evaluable patients, the conclusion would be that there is a 95% chance that the ORR in this protocol population would lie between 15.8% and 44.2%. The power for showing the response rate $>10\%$ at 5% two-sided alpha in 40 patients is 89%.	
All patients who have received any amount of study medication will be considered as evaluable for safety. Safety data will be summarized with descriptive statistics and frequency tables and will include AEs, hematology, coagulation, serum chemistry, urinalysis, vital signs, and ECG data. Laboratory values will be summarized by numerical value and toxicity grade.	

TABLE OF CONTENTS

SIGNATURES.....	2
HBI-8000-203 PROTOCOL SYNOPSIS	3
LIST OF ABBREVIATIONS AND DEFINITIONS OF TERMS	13
1.0 INTRODUCTION.....	15
1.1 Background Information	15
1.2 Histone Deacetylase as a Therapeutic Target in Cancer... 	15
1.3 Rationale for the Use of HBI-8000 for the Treatment of Cancer	16
1.3.1 Immunomodulatory Mechanisms Integrate with Cancer Cell Intrinsic Mechanisms of Cell Killing by HDACi.....	17
1.4 Nonclinical Studies.....	18
1.5 Clinical Pharmacology.....	19
1.5.1 Absorption	19
1.5.2 Distribution.....	20
1.5.3 Metabolism and Excretion.....	20
1.6 Clinical Studies.....	20

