5.9 Efficacy Analysis

The efficacy endpoints are the following:

Primary Endpoint:

- ORR(CR + PR)

Secondary Endpoint:

- ORR by disease subtype (see Section 2.5.1)
- Median duration of PFS
- Median DOR

Exploratory Endpoint

- Median duration of OS

Response rate endpoints (ORR and ORR by disease subtype) will be summarized by number and percentage of patients meeting the definition of ORR along with the corresponding exact 95% CI. Tumor response as assessed by imaging studies will be adjudicated by independent radiology reviewers. Tumor lesions, such as skin lesion, that cannot be monitored by imaging studies will be determined by independent oncology reviewers and contributed to overall disease response assessment. Both investigators reported and independently adjudicated outcomes will be reported. Primary analysis will be based on results from imaging studies and clinical data confirmed by Independent Central Review. Results from investigator assessment will also be reported. In addition, the ORR will be analyzed according to histology subtypes of PTCL. The subtypes reported by Central pathology review for each patient will be used for such analysis.

Time-to event endpoints (PFS, DOR, and OS) for entire study population will be summarized by Kaplan-Meier methods (median, 95% CI, number of events, number censored and Kaplan-Meier figures).

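### Minor, planning statement only: the 95% intervals for a 30% ORR in section 5.2 and the synopsis are unlabelled Wald limits, while section 5.9 prescribes exact limits, and the synopsis words the interval as a 95% chance

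*Combined protocol and SAP*

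**What the plan says.** Section 5.2 (Determination of Sample Size) sets the target: "The target best ORR for this study is 30%, on the basis of the ORR results that were obtained in study TG0902CDM". It sets the size: "For efficacy determination, 40 patients evaluable for efficacy per protocol criteria are required". It then gives the precision: "The 95% confidence interval (CI) for an ORR of 30% at a sample size of N=40 is expected to be between 15.8% and 44.2" per cent. A short table follows, introduced by "The 95% confidence interval for an objective response rate (assumed to be 30%) at various sample sizes are shown below", with rows for N=25 (12.0 to 48.0), N=30 (13.6 to 46.4), N=35 (14.8 to 45.2) and N=40 (15.8 to 44.2). No method is named for any of these limits. Beside them stands the power statement: "The power for showing the response rate >10% at 5% two-sided alpha in 40 patients is 89" per cent.

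Section 5.9 (Efficacy Analysis) says how ORR will be reported: number and percentage of responders "along with the corresponding exact 95% CI".

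The synopsis, under Statistical Procedures, assumes a 30% ORR in 40 evaluable patients and concludes that "there is a 95% chance that the ORR in this protocol population would lie between 15.8% and 44.2" per cent.

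**The concern.** A planning interval tells the reader what precision the chosen sample size will buy. Here it is computed by one method and the result will be reported by another, and nothing says so. A reader who takes section 5.2 at face value expects 12 of 40 to be reported as 15.8% to 44.2%. Under section 5.9 that result cannot produce that interval.

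The two methods also differ in shape. The Wald interval is symmetric about 30%. The exact interval is not: it reaches further above the estimate than below it.

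The synopsis sentence is a separate fault. It makes a probability statement about the ORR, whereas the 95% in a confidence interval describes the long-run behaviour of the procedure.

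What is at stake is the accuracy of the stated precision for N=40, and nothing further along.

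**Working it through.** **Inputs.** ORR 30%; N = 25, 30, 35 and 40; comparator 10%; two-sided 5% level; stated power 89% (all section 5.2). Exact 95% CI for the analysis (section 5.9).

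**Step 1: reproduce the printed intervals.** Wald limits are p ± 1.96·√(p(1−p)/N) with p = 0.30, so p(1−p) = 0.21.

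| N | 1.96·√(0.21/N), points | Wald limits (%) | Printed (%) |
|---|---|---|---|
| 25 | 17.96 | 12.04 to 47.96 | 12.0 to 48.0 |
| 30 | 16.40 | 13.60 to 46.40 | 13.6 to 46.4 |
| 35 | 15.18 | 14.82 to 45.18 | 14.8 to 45.2 |
| 40 | 14.20 | 15.80 to 44.20 | 15.8 to 44.2 |

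All four rows match to the printed decimal. At 12/40 the alternatives do not: Clopper-Pearson gives 16.6 to 46.5, Wilson 18.1 to 45.4, and Wald with continuity correction 14.55 to 45.45. The printed limits are uncorrected Wald limits.

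**Step 2: apply the prescribed method.** For x responders in N, the Clopper-Pearson lower limit is the 2.5% quantile of Beta(x, N−x+1), and the upper limit is the 97.5% quantile of Beta(x+1, N−x).

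| Result | Exact limits (%) | Exact width | Printed (%) | Printed width | Lower: exact − printed | Upper: exact − printed |
|---|---|---|---|---|---|---|
| 12/40 | 16.56 to 46.53 | 30.0 | 15.8 to 44.2 | 28.4 | +0.8 | +2.3 |
| 9/30 | 14.73 to 49.40 | 34.7 | 13.6 to 46.4 | 32.8 | +1.1 | +3.0 |

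At 12/40 the exact interval extends 13.4 points below 30% and 16.5 points above it.

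The other two rows have no exact counterpart at 30%, because 0.30 × 25 = 7.5 and 0.30 × 35 = 10.5 are not whole numbers of responders. The neighbouring counts give 12.07 to 49.39 (7/25), 14.95 to 53.50 (8/25), 14.64 to 46.30 (10/35) and 16.85 to 49.29 (11/35).

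**Step 3: check whether the power is affected.** The exact lower limit is 10.84% at 9/40 and 9.05% at 8/40, so under the section 5.9 method 9 is the smallest count that excludes 10%. P(X ≥ 9 | N = 40, 0.30) = 88.9%, which rounds to the stated 89%. P(X ≥ 9 | N = 40, 0.10) = 0.0155, within the 2.5% upper tail of a two-sided 5% test. The power statement is correct for a true ORR of 30% and agrees with the exact method.

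**Step 4: the synopsis sentence.** The most charitable reading is a prediction of the observed ORR when the true rate is 30%. An observed rate between 15.8% and 44.2% means 7 to 17 responders in 40, and that has probability 94.4%. Even on this reading the figure is only approximately 95%, and the sentence does not say that the observed rate is meant.

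**The case against.** The other side has a fair case. Each printed interval is correct for the normal approximation, so nothing was miscalculated. Section 5.2 describes what is expected under an assumed rate, while section 5.9 governs what is reported, and no passage says that the two must share a method. A formula-based table is also a natural way to show N=25 and N=35, where 30% cannot be observed. Against 10%, the only benchmark in the plan, the printed lower limit of 15.8% is the cautious one. The upper limit drives no decision.

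Most of this stands, and it is why the point is minor. It does not remove the point: the precision offered in support of N=40 is not what the prescribed analysis gives at the target result, and no label warns the reader.

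Three stronger readings are tempting, and the documents support none of them.

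- *The power is wrong or inconsistent.* A reader might carry the Wald method over to the test. The Wald lower limit at 9/40 is 9.56%, so 10 responders would be needed and power would be 80.4%. But section 5.9 prescribes exact limits, and the 89% agrees with them.
- *The reported interval will under-cover.* At a true ORR of 30% with N=40, Wald limits cover 93.0% of the time and exact limits 96.1%. No Wald interval is planned for the report, so the lower figure has no bearing on the results.
- *The plan needs a responder cutoff.* Section 5.1 says: "Statistical analysis for all safety, efficacy, and PK parameters will be primarily descriptive in nature". A printed cutoff could be taken for a success criterion that the plan does not set.

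**Conclusion.** The point holds as a minor correction to the planning statement. At 12/40 the stated interval is 1.6 points too narrow (28.4 against 30.0) and its upper limit 2.3 points too low; its lower limit is 0.8 points too low, which errs on the cautious side. At 9/30 the printed limits are 1.1 points (lower) and 3.0 points (upper) below the exact ones. The synopsis sentence is wrong as a description of a confidence interval.

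The conclusion takes the exact CI of section 5.9 to be Clopper-Pearson, the usual meaning of the term, and takes 30% at N=40 to be 12 responders. That the printed limits are Wald limits is inferred from the match in all four rows, since the protocol names no method. Sample size, the 89% power, the analysis method and the reported results are unaffected.

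**What to change.** - In section 5.2 and the synopsis, replace the N=40 interval with the exact one for 12/40: 16.6% to 46.5%. Change the N=40 row of the table to match.
- In the table, give 14.7% to 49.4% for N=30 (9/30).
- Label the N=25 and N=35 rows as normal approximations, with a note that 30% is not an observable count at those sizes and that the analysis will use exact limits.
- Replace the synopsis sentence with: *if 12 of 40 respond, the exact 95% CI is 16.6% to 46.5%*.
- Leave the 89% power statement as it is, and do not add a responder cutoff.

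The cost is a wording change in two places. The only downside is that the printed width and upper limit become slightly less favourable.
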